Study Design	
This is a Prospective, Vehicle Controlled, Double Blind, Multicenter, Randomized Phase II trial, comparing the effect of twice daily B244 application for 8 weeks vs. vehicle application on treatment of mild to moderate rosacea.
 
 • We will enroll approximately 130 subjects and complete 104 subjects. • At Screening and Baseline: 
 ○ All subjects must have diagnosis of mild to moderate Rosacea. ○ Subjects must have IGA score of 2-3 and CEA score of 2-3 to qualify for the study. • After screening and recruitment, participants will be randomized to active or vehicle application for 8 weeks. • Subjects will apply a total of 4 pumps of IP per application to the face twice-a-day • Randomization will be 1:1 B244 to Vehicle. • Subjects will be provided with cleanser and moisturizer to use for the duration of the study • All B244 randomized subjects will be treated at the dose of 4×10^9 cells/ml via spray application • Screening period will occur at Days -21 to -1 • Washout will occur after Screening visit (Days - 14 to -1) • Randomization will occur during the baseline visit for the study Efficacy will be assessed using Investigator Global Assessment (IGA) score, Clinician's Erythema Assessment (CEA) score, Patient Self-Assessment (PSA) score and patient reported Skindex 16. • Clinical assessments of response to treatment will be made at Week 1(Day 7), Week 4 (Day 28), and Week 8 (Day 56) • At Baseline visit, subjects will receive a kit containing the drug product. Each bottle will be used for 2 weeks. At Week 4, subjects will return the used bottles from the kit and will be issued a new kit of drug product to be used from Week 4 through Week 8. • Subjects will stop applying investigational product at Week 8 and will return investigational product at that visit.

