6.5.4 Per-Protocol (PP) Population

The PP population includes all randomized subjects who met all inclusion/exclusion criteria, were compliant with the assigned study treatment, returned to the study site for the primary endpoint visit within the specified window (± 2 days) OR discontinued from the study as a treatment failure, and did not have any major protocol violations.

Subjects who administered at least 50 % of IP, have at least one baseline and post baseline in clinic visit and did not have any major protocol violations.

Subjects who discontinued early from the study due to lack of treatment effect after completing at least eight weeks of treatment should be included in the mITT and PP population as treatment failures and the change in IGA and CEA from the baseline visit to the last completed visit prior to discontinuation due to lack of efficacy should be carried forward in the primary endpoint analysis. Subjects discontinued early for other reasons should be excluded from the PP population but included in the mITT population.

The results in the mITT population will be considered definitive for superiority of each active treatment to vehicle with those in the PP population considered supportive. Safety analyses will be performed using the Safety population.

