7.4 Study Drug Exposure

At Baseline visit, Subjects will receive a kit containing (2) two 30 ml white bottles. Each bottle will be used for 2 weeks. At Week 4, subjects will return the used bottles from the kit and will be issued a new kit of two 30mL white bottles to be used from Week 4 through Week 8.

The cumulative amount of study drug exposure will be estimated by calculating the difference between the weight of the 2 bottles of drug at the time the drug was dispensed at Baseline/Week 4 and the weight of the 2 bottles at Week 4/Week 8. Differences will be summed together.

The amount of product used per day will be estimated by dividing the change by the number of days the subject was on treatment. These weights will be compared to the weight of the product that would be used if the subject was compliant with the protocol. Percent compliance will be calculated as follows:

$$\text{Percent compliance} = \left[\frac{\text{Net Weight of Study Drug}}{(1.12\text{g/day} * \text{Number of days in the study})} \right] * 100\%$$

xx.xx g

The number of days the subject administered study drug, the amount of product used, and the percent compliance will be summarized by treatment group and presented in a by-subject data listing. The subject listing will also include by-visit IP weights. Percent compliance will be calculated only for subjects who returned the study drug at the end of the treatment. In the listing, subjects who withdrew from the study early will be flagged.

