Disposition	B244 Topical Spray n (%)	Placebo n (%)	All Patients n (%)
Randomized	xx (xx.x)	xx (xx.x)	xx (xx.x)
Treated	xx (xx.x)	xx (xx.x)	xx (xx.x)
Completed	xx (xx.x)	xx (xx.x)	xx (xx.x)
Completed Week 1	xx (xx.x)	xx (xx.x)	xx (xx.x)
Completed Week 4	xx (xx.x)	xx (xx.x)	xx (xx.x)
Completed Week 8	xx (xx.x)	xx (xx.x)	xx (xx.x)
Completed Week 12	xx (xx.x)	xx (xx.x)	xx (xx.x)
Discontinued	xx (xx.x)	xx (xx.x)	xx (xx.x)
Withdrawal of consent	xx (xx.x)	xx (xx.x)	xx (xx.x)
In the opinion of the Investigator, it is not in the subject's best interests to continue in the study	xx (xx.x)	xx (xx.x)	xx (xx.x)
Pregnancy	xx (xx.x)	xx (xx.x)	xx (xx.x)
Occurrence of an Adverse Event (AE) or Serious Adverse Event (SAE), which, in the opinion of the Investigator warrants discontinuation of the subject from the study	xx (xx.x)	xx (xx.x)	xx (xx.x)
The subject is lost to follow-up	xx (xx.x)	xx (xx.x)	xx (xx.x)
Other	xx (xx.x)	xx (xx.x)	xx (xx.x)

NOTE: The percentages are based on the number of Randomized subjects.

Subjects may have more than one reason for discontinuation, and they are counted more than once.

Snapshot Data DD-MMM-YYYY

Source: <Dataset>

Program Name: <Pgm name>

Table 14.1.1.3
 Analysis Population and Exclusions
 All Subjects

Number of Subjects	B244 Topical Spray n (%)	Placebo n (%)	All Patients n (%)
Enrolled	xx	xx	xx
Randomized	xx	xx	xx
Included in Safety Population	xx	xx	xx (xx.x%)
Reasons for Exclusion from Safety Population			
	xx	xx	xx (xx.x%)
	xx	xx	xx (xx.x%)
Included in Full Analysis Set	xx	xx	xx (xx.x%)
Reasons for Exclusion from Safety Population			
	xx	xx	xx (xx.x%)
Included in Per Protocol Population	xx	xx	xx (xx.x%)
Reasons for Exclusion from Per Protocol Population			
Lost To Follow Up	xx	xx	xx (xx.x%)
Major Deviation	xx	xx	xx (xx.x%)
Not 50% Ip Compliant	xx	xx	xx (xx.x%)
Screen Failure	xx	xx	xx (xx.x%)
Withdrawal of Consent By Subject	xx	xx	xx (xx.x%)

NOTE: The percentages are based on the number of All subjects.

Snapshot Data DD-MMM-YYYY

Program Name: <Pgm name>

Source: <Dataset>

Table 14.1.2.1
 Summary of Protocol Deviations (PD)/Violations (PV)
 mITT Population

Deviation/Violation Description of Violation/deviation	Deviation/Violation Category “Major” or “Minor”	B244 Topical	Placebo	All
		Spray n (%) xx	n (%) xx	Patients n (%) xx

NOTE: The percentages are based on the number of ITT Population.

Source: <Dataset>

Snapshot Data DD-MMM-YYYY
 Program Name: <Pgm name>

Repeat for Safety Population

Table 14.1.3.1

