If No, Applications Missed				
Missed Applications	N	xx	xx	xx
	Mean (SD)	xx.x (xx.xxx)	xx.x (xx.xxx)	xx.x (xx.xxx)
	CV	xx.x	xx.x	xx.x
	Median	xx.x	xx.x	xx.x
	Min, Max	xx.x, xx.x	xx.x, xx.x	xx.x, xx.x

 Applications: Number of applications per patients/day
 (expected 4 Pumps twice a Day)

 Snapshot Data DD-MMM-
 YYYY

CRF pages 30

 Compliance: The expected amount of study drug used
 per week is approximately 7.84 g/week for 8
 sprays/application per day

 Source:
 <Dataset>

 Program Name: <Pgm
 name>

Table 14.1.7.2
 Summary of Percent Compliance based on Cumulative Net Weight of Study Drug
 Safety Population

Protocol: RB244-001
 Confidential

STATISTICAL ANALYSIS PLAN

 Version 2
 02-Apr-19

Statistic	B244 Topical			All Patients n (%)
	Spray n (%)	Placebo n (%)		
Cumulative Net Weight of Study Drug				
N	xx	xx	xx	xx
Mean (SD)	xx.x (xx.xxx)	xx.x (xx.xxx)	xx.x (xx.xxx)	xx.x (xx.xxx)
CV	xx.x	xx.x	xx.x	xx.x
Median	xx.x	xx.x	xx.x	xx.x
Min, Max	xx.x, xx.x	xx.x, xx.x	xx.x, xx.x	xx.x, xx.x
Percent Compliance greater than 50%				
Yes	N (%)	xx (xx.x)	xx (xx.x)	xx (xx.x)
No	N (%)	xx (xx.x)	xx (xx.x)	xx (xx.x)

Applications: Number of applications per patients/day (expected 4 Pumps twice a Day)

Snapshot Data DD-MMM-YYYY

CRF pages 30

The cumulative amount of study drug exposure will be estimated by calculating the difference between the weight of the 2 bottles of drug at the time the drug was dispensed at Baseline/Week 4 and the weight of the 2 bottles at Week 4/Week 8. Differences will be summed together.

Program Name: <Pgm name>

Source: <Dataset>

% Compliance: The net weight of study drug divided by 1.12g/Day * Number of Days in the Study

Table 14.1.8
 Summary of Prior or Concomitant Medications,
 Safety Population

WHO-DD ATC Class Level 1 WHO-DD ATC Class Level 2 WHO-DD Preferred Term	B244 Topical Spray n (%)	Placebo n (%)	All Patients n (%)
Number of subjects with at least one prior medication	xx (xx.x)	xx (xx.x)	xx (xx.x)
WHO-DD ATC Class Level 1	xx (xx.x)	xx (xx.x)	xx (xx.x)

Protocol: RB244-001
 Confidential

STATISTICAL ANALYSIS PLAN

 Version 2
 02-Apr-19

WHO-DD ATC Class Level 2	xx (xx.x)	xx (xx.x)	xx (xx.x)
WHO-DD Preferred Term 1	xx (xx.x)	xx (xx.x)	xx (xx.x)
WHO-DD Preferred Term 2	xx (xx.x)	xx (xx.x)	xx (xx.x)
etc.			
WHO-DD ATC Class Level 1	xx (xx.x)	xx (xx.x)	xx (xx.x)
WHO-DD ATC Class Level 2	xx (xx.x)	xx (xx.x)	xx (xx.x)
WHO-DD Preferred Term 1	xx (xx.x)	xx (xx.x)	xx (xx.x)
WHO-DD Preferred Term 2	xx (xx.x)	xx (xx.x)	xx (xx.x)
etc.			

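### SAP percent compliance divides by days in the study, not the treatment period: at 84 days a perfect 8-week user scores 66.7% and the 50% cut becomes 75% of expected use

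*SAP*

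**What the plan says.** SAP version 2, Section 7.4 (Study Drug Exposure), sums the bottle-weight differences from Baseline to Week 4 and from Week 4 to Week 8. It then uses two different day counts:

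- Daily use is obtained by "dividing the change by the number of days the subject was on treatment", and the result is compared with "the weight of the product that would be used if the subject was compliant with the protocol".
- Percent compliance is the net weight divided by 1.12 g/day times the "Number of days in the study". The footnote to Table 14.1.7.2 repeats this: "The net weight of study drug divided by 1.12g/Day * Number of Days in the Study".

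The SAP does not define the second day count. SAP version 1 has the same formula.

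On duration, the version 2 synopsis says "Subjects will stop applying investigational product at Week 8 and will return investigational product at that visit". The same synopsis gives participation as up to 84 days, plus or minus 2. Section 6.7.6 also describes a study period running from randomization to Week 12.

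The 50% level appears in three places:

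- the PP definition in Section 6.5.4: "Subjects who administered at least 50 % of IP"
- the PP exclusion reasons in Table 14.1.1.3: "Not 50% Ip Compliant"
- a row of Table 14.1.7.2: "Percent Compliance greater than 50" (per cent)

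A secondary point also bears on PP membership. The SAP synopsis lists three or more facial inflammatory lesions as an exclusion, while Protocol 5.1.1 requires 3 to 20. The hormonal-therapy window is 90 days in the SAP synopsis and 30 days in Protocol 5.1.2.

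**The concern.** The numerator can only contain product used in the 8-week dosing period. If the denominator runs to Week 12, it expects product to be used in four weeks when the protocol allows none. Every completer's compliance is then understated by one third.

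Three consequences follow on that reading:

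- **Reported compliance.** The Safety-population compliance table would describe a well-adhering trial as a poorly adhering one.
- **PP membership.** Section 7.4 holds the only compliance formula in the SAP, so it is the likely source of the 50% flag. Completers with true use of at least 50% but below 75% would fall under the cut.
- **Dependence on follow-up.** The same grams used give a lower score to a subject who attends Week 12 than to one who leaves at Week 8. The score then reflects follow-up attendance as well as adherence.

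The eligibility mismatch matters because PP requires all inclusion and exclusion criteria to be met and a by-subject listing of unmet criteria is planned. No subject can satisfy both lesion-count texts.

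**Working it through.** **Inputs**

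- Expected daily use: 1.12 g (SAP 7.4).
- Expected weekly use: 7.84 g (footnote to SAP Table 14.1.7.1).
- Treatment period: 8 weeks = 56 days, with a Week 8 visit window of ±2 days.
- Study participation: 84 days, with a Week 12 visit window of ±2 days. Using this as the days in the study is an assumption.
- Threshold: 50%.

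**The SAP's own figure.** 1.12 × 7 = 7.84 g/week, which agrees with the Table 14.1.7.1 footnote.

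**Formulas**

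- Percent compliance = net weight / (1.12 × days) × 100.
- Net weight of a perfect user = 1.12 × 56 = 62.72 g.
- Cut as a share of expected use = 0.5 × (1.12 × days) / 62.72.

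**Results under each reading of the day count**

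| Days in denominator | Denominator (g) | Perfect user's score | 50% cut (g) | Cut as share of expected use |
|---|---|---|---|---|
| 56 (treatment) | 62.72 | 100% | 31.36 | 50% |
| 84 (to Week 12) | 94.08 | 66.7% | 47.04 | 75% |
| 105 (adding a 21-day screening period; assumption) | 117.60 | 53.3% | 58.80 | 93.75% |

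**Visit windows, reading to Week 12.** With treatment of 54 to 58 days and study time of 82 to 86 days:

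- Perfect user's score: 54/86 = 62.8% to 58/82 = 70.7%.
- Cut: 0.5 × 82/58 = 70.7% to 0.5 × 86/54 = 79.6% of expected use.

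**Same use, different attendance.** A subject using 60% of expected product uses 0.6 × 62.72 = 37.63 g.

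- Attends Week 12 (Day 84): 37.63/94.08 = 40%.
- Leaves at Week 8 (Day 56): 37.63/62.72 = 60%.

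**Choosing the replacement day count.** Take a subject who applies fully to Day 28, stops, and stays in the study to Day 84. Net weight is 1.12 × 28 = 31.36 g.

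- As written, at 84 days: 28/84 = 33%.
- First to last application: 28/28 = 100%, which hides the early stop.
- Treatment period to the Week 8 visit: 28/56 = 50%.

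That last score passes the PP wording (at least 50%) and fails the Table 14.1.7.2 wording (greater than 50%), so the two need to agree.

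**The case against.** The strongest reply is that Section 7.4, read as a whole, points to treatment days. It divides daily use by time on treatment, compares with protocol-compliant use, and collects weights only to Week 8. A sensible programmer might therefore use 56 days, and nothing would be distorted. This is a fair reading and makes the size conditional. It does not settle the matter, because 7.4 has its own terms for treatment time and the formula uses a different one.

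Other objections, and what stands of each:

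- **84 days is only one reading.** True. Counting screening gives 105 days, but that makes the error larger.
- **Section 6.5.4 does not cite the 7.4 formula.** True. The link to PP is inferred from the shared 50% level and the exclusion reason in Table 14.1.1.3.
- **The attendance example mostly falls outside PP.** Largely right. Early leavers are excluded from PP unless they left for lack of treatment effect. The example therefore applies to Table 14.1.7.2 and, within PP, to lack-of-effect leavers who are retained.
- **The threshold wordings differ only at exactly 50%.** True, and this will rarely matter with weighed bottles. Aligning them costs nothing.
- **The eligibility mismatch is a separate matter.** It is not about the denominator, but it is real and affects the same population. The two items are not a full list: the SAP synopsis also has an exclusion for MAO inhibitors and other listed drugs that the protocol lacks, and a 1-week rather than 2-week washout for topical acne medication.
- **The stakes are modest.** Agreed: the primary objective is descriptive safety, all efficacy endpoints are exploratory, and mITT is definitive.

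**Conclusion.** The concern holds. As written, the formula conflicts with the comparison that its own section describes. If days in the study means the 84 days of participation, a perfect completer scores 66.7% (62.8% to 70.7% across visit windows) and the 50% cut becomes 75% of expected use (70.7% to 79.6%). If the term means treatment days, there is no numerical error and only the wording needs correcting.

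The effect on PP further assumes that the 50% rule is computed from this formula. A perfect user passes under every reading examined, the number of subjects affected cannot be known from the documents, and the definitive mITT results are untouched. The correction is worth making because two competent programmers could produce different compliance tables and different PP sets from the same text.

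**What to change.** 1. In SAP 7.4 and the Table 14.1.7.2 footnote, replace the day count in the formula with the number of days in the treatment period. Define it as first application to the Week 8 visit (planned 56 days), or to the Early Termination visit if earlier. It excludes post-treatment follow-up and is not shortened when a subject stops applying but remains in the study.
2. In 6.5.4, state that the PP 50% rule uses this figure.
3. Use one threshold wording in 6.5.4 and Table 14.1.7.2.
4. Separately, reconcile the SAP synopsis with the protocol on lesion count and the hormonal-therapy window, and check the rest of the eligibility list. State that PP eligibility and the deviation listings use the criteria of the protocol under which subjects were enrolled.

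The cost is SAP wording and one variable in the compliance derivation. Nothing changes for sites or subjects.

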10.1.2 Efficacy

Display Number	Title	Population	Unique/Repeat
14.2.1.1	Change from baseline in IGA score by Visit	mITT	Unique
14.2.1.2	Change from baseline in IGA score by Visit	PP	Repeat
14.2.2.1	Change from baseline in CEA score by Visit	mITT	Repeat
14.2.2.2	Change from baseline in CEA score by Visit	PP	Repeat
14.2.3.1	Change from baseline in PSA score by Visit	mITT	Repeat
14.2.3.2	Change from baseline in PSA score by Visit	PP	Repeat
14.2.4.1	Summary of Change from baseline in Skindex 16 score by Visit	mITT	Unique
14.2.4.2	Summary of Change from baseline in Skindex 16 score by Visit	PP	Repeat
14.2.5.1	Change from baseline in Telangiectasia score by Visit	mITT	Repeat
14.2.5.2	Change from baseline in Telangiectasia score by Visit	PP	Repeat
14.2.6.1	Summary of 2-grade improvement in IGA score from baseline to the end of treatment.	mITT	Unique
14.2.6.2	Summary of 2-grade improvement in IGA score from baseline to the end of treatment	PP	Repeat
14.2.7.1	Summary of 2-grade improvement in CEA score from baseline to the end of treatment	mITT	Repeat
14.2.7.2	Summary of 2-grade improvement in CEA score from baseline to the end of treatment .	PP	Repeat
14.2.8.1	Summary of IGA score of 0/1 at End of Treatment.	mITT	Unique
14.2.8.2	Summary of IGA score of 0/1 at End of Treatment.	PP	Repeat
14.2.9.1	Summary of CEA score of 0/1 at End of Treatment.	mITT	Repeat
14.2.9.2	Summary of CEA score of 0/1 at End of Treatment.	PP	Repeat
14.2.10.1	Summary of Sensitivity Analysis for Change from Baseline Score of IGA	mITT	Unique
14.2.10.2	Summary of Sensitivity Analysis for Change from Baseline Score of CEA	mITT	Repeat
14.2.10.3	Summary of Sensitivity Analysis for Change from Baseline Score of PSA	mITT	Repeat

Table 14.2.1.1
 Change from baseline in IGA Score by Visit.
 mITT Population

Visit	B244 Topical Spray N (xxx)	Placebo N (xxx)	All Patients N (xxx)
Week 1			
Change from Baseline			
1-grade	n (%)		
2-grade	n (%)		
3-grade	n (%)		
Repeat for all the visits			

CRF pages
 Source: <Dataset>
 Snapshot Data DD-MMM-YYYY
 Program Name: <Pgm name>

Repeat for CEA and PSA & Telangiectasia Score for mITT & PP population.

Table 14.2.4.1
 Summary of Change from baseline in Skindex 16 score by Visit
 mITT Population

Visit	B244 Topical Spray N (xxx)	Placebo N (xxx)	All Patients N (xxx)
Baseline			
N	xx	xx	xx
Mean (SD)	xx.x (xx.xxx)	xx.x (xx.xxx)	xx.x (xx.xxx)
CV	xx.x	xx.x	xx.x
Median	xx.x	xx.x	xx.x
Min, Max	xx.x, xx.x	xx.x, xx.x	xx.x, xx.x
Change from Baseline at Week 1			
N	xx	xx	xx
Mean (SD)	xx.x (xx.xxx)	xx.x (xx.xxx)	xx.x (xx.xxx)
CV	xx.x	xx.x	xx.x
Median	xx.x	xx.x	xx.x
Min, Max	xx.x, xx.x	xx.x, xx.x	xx.x, xx.x

Repeat for All weeks

Final Analysis for Week 12	
Differences of LS Means	X.XXXX
SE	X.XXXX
CI	(X.XXXX, X.XXXX)
P-value	X.XXXX

SE: Standard Error of the LS Means

CRF pages

Snapshot Data DD-MMM-YYYY

Source: <Dataset>

Program Name: <Pgm name>

Repeat for PP population.

Table 14.2.10.1
 Summary of Sensitivity Analysis for Change from Baseline Score of IGA
 mITT Population

Imputation	B244 Topical Spray N (xxx)	Placebo N (xxx)	All Patients N (xxx)
Imputation#1			
N	xx	xx	xx
Mean (SD)	xx.x (xx.xxx)	xx.x (xx.xxx)	xx.x (xx.xxx)
Q1, Q3	xx.x, xx.x	xx.x, xx.x	xx.x, xx.x
Imputation#2			
N	xx	xx	xx
Mean (SD)	xx.x (xx.xxx)	xx.x (xx.xxx)	xx.x (xx.xxx)
Q1, Q3	xx.x, xx.x	xx.x, xx.x	xx.x, xx.x
Repeat for all imputations			
Analysis Summary			
Mean (SD)			x.xx, x.xx
CI			x.xxx
P-Value			

SD: Standard Error of the Parameters

CI: Confidence Interval

Repeat for CEA & PSA.

 CRF pages
 Source: <Dataset>

 Snapshot Data DD-MMM-YYYY
 Program Name: <Pgm name>

Table 14.2.6.1
 Summary of 2-grade improvement in IGA score from baseline to the end of treatment.
 mITT Population

	B244 Topical Spray N (xxx)	Placebo N (xxx)	All Patients N (xxx)
Subjects with 2-Grade improvement from Baseline to End of Treatment	n (%)	n (%)	n (%)
Risk Difference			x.xxx
CI			(x.xx, x.xx)
P-value			x.xxxx

CI: Confidence Interval

Source: <Dataset>

 Snapshot Data DD-MMM-YYYY
 Program Name: <Pgm name>

Repeat for PP Population and for CEA (mITT & PP).

Table 14.2.8.1
 Summary of IGA score of 0/1 at End of Treatment.
 mITT Population

	B244 Topical Spray N (xxx)	Placebo N (xxx)	All Patients N (xxx)
Subjects with Score of 0/1 at End of Treatment	n (%)	n (%)	n (%)
Risk Difference			x.xxx
CI			(x.xx, x.xx)
P-value			x.xxxx

CI: Confidence Interval

Snapshot Data DD-MMM-YYYY

Source: <Dataset>

Program Name: <Pgm name>

Repeat for PP Population and for CEA (mITT & PP)

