x.xxxx

SE	x.xxxx
CI	(x.xxxx, x.xxxx)
P-value	x.xxxx

SE: Standard Error of the LS Means

P- Value: Probability of Change from Baseline at Week 12

CRF pages

Snapshot Data DD-MMM-YYYY

Source: <Dataset>

Program Name: <Pgm name>

Repeat for PP population.

Table 14.2.5
 Summary of Sensitivity Analysis for the Absolute Scores of IGA, CEA & PSA
 mITT Population

Imputation	B244 Topical Spray N (xxx)	Placebo N (xxx)	All Patients N (xxx)
Imputation#1			
N	xx	xx	xx
Mean (SD)	xx.x (xx.xxx)	xx.x (xx.xxx)	xx.x (xx.xxx)
Q1, Q3	xx.x, xx.x	xx.x, xx.x	xx.x, xx.x
Imputation#2			
N	xx	xx	xx
Mean (SD)	xx.x (xx.xxx)	xx.x (xx.xxx)	xx.x (xx.xxx)
Q1, Q3	xx.x, xx.x	xx.x, xx.x	xx.x, xx.x
Repeat for all imputations			
Analysis Summary			
Parameter1			xx.x (xx.xxx)
Mean (SD)			x.xx, x.xx
CI			x.xxx
P-Value			
Parameter2			
Parameter3			

 SD: Standard Error of the Parameters

P- Value: Significance of the Parameters effecting the imputation

CRF pages

Snapshot Data DD-MMM-YYYY

Source: <Dataset>

Program Name: <Pgm name>

Table 14.2.6.1

Summary of 2-grade improvement in IGA score from baseline to the end of treatment (Week 8).
 mITT Population

	B244 Topical Spray N (xxx)	Placebo N (xxx)	All Patients N (xxx)
Subjects with 2-Grade improvement from Baseline to Week 8	n (%)	n (%)	n (%)
Risk Difference			x.xxx
CI			(x.xx, x.xx)
One Sided P-value			x.xxxx

CI: Confidence Interval

P-value: Probability of Superiority from the Placebo

Snapshot Data DD-MMM-YYYY

Source: <Dataset>

Program Name: <Pgm name>

Repeat for PP Population and for CEA (mITT & PP).

Table 14.2.8.1

Summary of Treatment success with IGA score of 0 or 1.
 mITT Population

	B244 Topical Spray N (xxx)	Placebo N (xxx)	All Patients N (xxx)
Subjects with IGA Score of 0/1 at End of Treatment	n (%)	n (%)	n (%)
CI			(x.xx, x.xx)
P-value			x.xxxx

CI: Confidence Interval

P-value: Probability of achieving Treatment Success defined as a score of 0/1.

Snapshot Data DD-MMM-YYYY

Source: <Dataset>

Program Name: <Pgm name>

Repeat for PP Population and for CEA (mITT & PP)

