8.3 Efficacy Analysis

All efficacy endpoints are exploratory endpoints.

Assessment of Superiority:

- IGA treatment success, defined as “clear” or “almost clear” with a 2-grade improvement in IGA score from baseline to the end of treatment (Week 8).
- CEA treatment success, defined as “clear” or “almost clear” with a 2-grade improvement in CEA score from baseline to the end of treatment (Week 8).

Superiority will be based on the proportion of subjects for whom treatment was successful. The comparison will be through a continuity-corrected Z-tests. The Evaluable Period for the outcome variables will be weeks 1, 4, 8 and 12. The superiority of the drug over the vehicle will be tested at week 8 based on the probability of

improvement from baseline with a continuity-corrected Z-tests comparing the change from baseline of treatments vs Placebo. For all other evaluable periods, descriptive statistics for the change from baseline will be shown.

The null and alternative statistical hypotheses for the primary effectiveness endpoints are given by:

(*H*₀): The null hypothesis is that the probability of improving (baseline to week 8) with drug T (*Pr*_T) is less than or equal to the probability of improving with vehicle (*Pr*_V).

$$H_0: Pr_T - Pr_V \leq 0; Pr_T$$

(*H*_a): The alternative hypothesis is that the probability of improving with drug T (*Pr*_T) is greater than to the probability of improving with vehicle (*Pr*_V).

$$H_a: Pr_T > Pr_V; Pr_T - Pr_V > 0$$

For testing the superiority, the following SAS code will be used:

```
proc freq data = dataset;
  tables treat*outcome/riskdiff (equal);
run;
```

- Change of Skindex 16 patient reported outcome from Baseline to Week 1, Week 4, Week 8 and Week 12

The change from baseline score of Skindex-16 will be compared among treatments at Week 12 using an ANOVA, to test the Skindex 16 score change from Baseline to Week 12 for the two treatments. Also, descriptive stats will be used to assess the change from Baseline to Week 1, 4, 8 & 12.

- Change of IGA score at Baseline to Week 1, Week 4, Week 8 and Week 12.
- Change of CEA score at Baseline to Week 1, Week 4, Week 8 and Week 12.
- Change of PSA score at Baseline to Week 1, Week 4, Week 8 and Week 12.

Descriptive stats will be used to show the change from Baseline to Week 1, 4, 8 & 12.

- Supplemental Analysis

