8.4 Sensitivity Analysis

A sensitivity analysis will be performed by Multiple Imputation Regression Analysis using the following factors: treatment, age, gender, race, baseline IGA, baseline CEA, baseline

PSA, smokers/non-smokers and the results of the same variable from previous visits. The Proc MI SAS code will be used to perform the analysis based on the mentioned factors.

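### SAP v2's multiple-imputation tables attach a p-value to a pooled mean change with no B244-minus-vehicle contrast, model or null, so they do not show whether dropout alters the treatment comparison

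*SAP*

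**What the plan says.** SAP v2 section 8.3 frames efficacy as a comparison of arms, with the alternative "H_a: Pr_T > Pr_V; Pr_T - Pr_V > 0", tested at Week 8 on the proportion with treatment success. For the IGA, CEA and PSA change scores the same section plans descriptive statistics only. Section 6.7.4 imputes nothing in the main analyses and leaves missing data to a multiple-imputation sensitivity analysis.

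Section 8.4 describes that analysis by listing factors (treatment, age, gender, race, baseline scores, smoking, earlier visits) and adding: "The Proc MI SAS code will be used to perform the analysis based on the mentioned factors". The output is Table 14.2.10.1, "Summary of Sensitivity Analysis for Change from Baseline Score of IGA", with the instruction "Repeat for CEA & PSA". It shows N, mean (SD) and quartiles by arm for each imputation. A summary block follows with three labels: mean (SD), CI and p-value. The footnote reads "SD: Standard Error of the Parameters". Nothing says what the p-value tests.

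Other inferential shells in section 10.1.2 do name a contrast. The Skindex-16 table has "Differences of LS Means", and the 2-grade-improvement and score-0/1 tables have "Risk Difference".

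**The concern.** A change-from-baseline mean printed with its standard error, CI and p-value, and with no difference row, is ordinarily a test of that mean against zero. That is not the trial's question. If both arms improve, such a p-value can be small when B244 and vehicle do equally well, and a reader could take it as evidence that the B244 result survives missing data.

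The accompanying text does not rescue the shell. Repeating the main analysis on the imputed data is not a default that an analyst can fall back on, because section 8.3 plans no between-arm test of mean change. Testing change against zero is also not foreign to this SAP: the supplemental analysis in 8.3 calls for p-values for change to Week 8 within each arm.

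At stake is the one analysis meant to show whether the assumed 20% dropout affects the comparison.

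**Working it through.** The shells hold placeholders only, so there is no stated result to reproduce. The one related figure, enrolment, does reproduce: 104 / (1 - 0.20) = 130.

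**Step 1. Shells side by side (SAP v2, 10.1.2).**

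| Table | Summary estimate | Contrast named? |
|---|---|---|
| 14.2.4.1 Skindex-16 | difference of LS means | yes |
| 14.2.6.1 two-grade improvement | risk difference | yes |
| 14.2.8.1 score 0/1 | risk difference | yes |
| 14.2.10.1-3 multiple imputation | mean | no |

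In SAP v1 the corresponding shell (Table 14.2.5) defined its p-value as "P- Value: Significance of the Parameters effecting the imputation", which is not stated as a treatment comparison. SAP v2 dropped that footnote and the parameter rows and put no contrast in their place. The same revision added a risk difference to Table 14.2.8.1, which lacked one in v1.

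**Step 2. What follows if the p-value is a test of the pooled mean.** Inputs from the documents: two-sided 5% level (SAP 6.4), 104 completers and 130 enrolled at 1:1 (SAP 4.3), 20% dropout. The documents give no mean or SD of change, so these are assumed over a range. Both arms are given the same distribution throughout.

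Exact calculation: one-sample t-test of mean change = 0, n = 104, noncentrality = mean / (SD / √n). For a mean of 0.2 and SD 0.8, this is 0.2 / (0.8 / 10.2) = 2.55. Probability of p < 0.05:

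| Common improvement (grades) | SD 0.6 | SD 0.8 | SD 1.0 |
|---|---|---|---|
| 0 | 5% | 5% | 5% |
| 0.1 | 39% | 24% | 17% |
| 0.2 | 92% | 71% | 52% |
| 0.3 | 99.9% | 97% | 86% |
| 0.5 | >99.8% | >99.8% | >99.8% |

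**Step 3. Simulation with imputation.** 65 per arm, 20% missing at random, regression imputation with treatment in the model. Results were combined by Rubin's rules: estimate = average over M imputations; variance T = W + (1 + 1/M)B, where W is the average within-imputation variance and B the between-imputation variance. Rows a-d use 2,000 trials and M = 10; rows e-f use 1,500 trials and M = 5.

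| Row | Worse / same / 1 better / 2 better (%) | Mean improvement | Pooled mean p < 0.05 | B244 minus vehicle p < 0.05 |
|---|---|---|---|---|
| a | 20 / 60 / 20 / 0 | 0 | 4.8% | 4.6% |
| b | 20 / 50 / 20 / 10 | 0.2 | 63% | 5.0% |
| c | 10 / 60 / 20 / 10 | 0.3 | 97% | 6.2% |
| d | 10 / 50 / 30 / 10 | 0.4 | 99.8% | 4.9% |
| e | 10 / 70 / 15 / 5 | 0.15 | 68% | 4.6% |
| f | 5 / 60 / 25 / 10 | 0.4 | 100% | 5.5% |

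The mean in row e is -0.10 + 0.15 + 2 × 0.05 = 0.15, and its SD is √(0.10 + 0.15 + 4 × 0.05 - 0.15²) = √0.4275 = 0.65. With n = 104 the noncentrality is 0.15 / (0.65 / 10.2) = 2.35, or roughly 65% rejection, in line with the simulated 68%.

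**Step 4. Is a common improvement plausible?** Section 8.1 assumes 10% response on vehicle. If response means a two-grade improvement (8.1 does not define it), those subjects alone add 0.10 × 2 = 0.2 grade to the vehicle mean, before counting one-grade gains or worsening.

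**The case against.** The strongest reply is that the SAP never writes a null for this p-value. The footnote speaks of parameters, section 8.4 calls the method a regression analysis, treatment heads its factor list, and SAP v1 had several numbered parameter rows. The single v2 row could therefore be a retained treatment coefficient. In the text as read from the PDF, the values in the summary block also do not line up with their labels, so a row may have been lost in extraction. Pooling is implied by the layout even though no procedure is named. The simulations show what a one-sample test would do, not that one is specified.

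Much of this stands. The null is an inference, so a reader who concludes that the SAP prescribes a test of mean change = 0 goes further than the documents do. What does not stand is the idea that the gap is harmless. No row, label or footnote provides for a treatment coefficient, and a mean is not a description of one. The position of the value in the all-patients column settles nothing, because the risk differences sit there too.

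A reader might also infer that the p-value would be significant whatever B244 does. It would not: with identical arms it is nominal at zero mean change and rejects in only 17-39% of trials at 0.1 grade. Entry at IGA and CEA 2-3 does not by itself establish how large the average improvement will be.

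Finally, efficacy is exploratory, the main responder tables carry explicit risk differences, and per-imputation means are printed by arm, so a marked difference in mean change would be visible even though it is not tested.

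**Conclusion.** The point holds as a gap in the estimate, with a likely wrong test as its consequence. Tables 14.2.10.1-3 and section 8.4 attach a p-value to a pooled mean change without a contrast, a post-imputation model or a null. The most natural reading is a test of mean change = 0, and no reading supplies a treatment comparison.

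The size depends on that reading and on assumed change distributions with data missing at random. With identical arms, p < 0.05 in about 60-70% of trials at 0.15-0.2 grade of common improvement, near 100% at 0.4, and about 5% at zero. A between-arm contrast on the same imputed data stays at 4.6-6.2%.

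A contrast of mean changes alone would still not test the robustness of the responder comparison in 8.3. Because efficacy is exploratory the severity is modest, but the change should be made before the tables are programmed.

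**What to change.** - In section 8.4 and Tables 14.2.10.1-3, replace the summary rows with the B244-minus-vehicle difference at Week 8, its standard error, 95% CI and p-value. State the between-arm model, fit it in each imputed data set, and combine by Rubin's rules (Proc MIANALYZE).
- For IGA and CEA, also derive treatment success from the imputed Week 8 scores and report the combined risk difference, so that the check matches the test in 8.3. Say how non-integer imputed scores are mapped to grades.
- Drop any p-value for an overall mean or an imputation-model parameter, and label the standard error as such rather than as SD.

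The cost is SAP wording, one revised shell with its repeats, an added risk-difference summary for IGA and CEA, and a short combining step in the program. No new data are needed.
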